9.2.2 Seriousness

The following guidelines will be used to describe seriousness.

- results in death,
- is life-threatening,
- requires inpatient hospitalization or prolongation of existing hospitalization,
- results in persistent or significant disability/incapacity,
- is a congenital anomaly/birth defect
- medical important event

Hospitalization is a seriousness criterion. The following admission to hospitals should not be recorded and reported as an SAE:

- Hospital admission due to administrative reasons
- Hospital admission prior to signing the ICF
- Hospital admission not associated with a worsening of a preexisting condition
- Hospital admission without an AE, e.g. elective hospitalization and surgery for treatment of the underlying AML/MDS disease including transfusions

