1.3.1 Justification for a protocol amendment

A decision was made to increase the initial frequency of dosing from once in █ weeks to once in █ weeks for at least the first █ cycles █
 █ The justification for this is discussed also in section 7.6 █
 █.

████████████████████ The most frequently recorded AEs were under the following Medical Dictionary for Regulatory Activities (MedDRA) system organ classes: infections and infestations, gastrointestinal disorders, general disorders and administration site conditions, and respiratory, thoracic and mediastinal disorders. This information is consistent with the safety profile of imetelstat according to the current version of the IB. A total of 30 SAEs were recorded in █████ patients, of which █████ were assessed as being at least possibly related to imetelstat. Of these █████ █████ were assessed as unexpected and were reported as SUSARs.

According to the safety data collected, no major change to the risk assessment was seen and there was no cause to conclude that imetelstat should not be used in patients with MDS/AML.

Given the short half-life of imetelstat, there is reason to believe that an increased frequency of dosing may be beneficial to patients

Given that no new safety signals to argue stopping imetelstat therapy were seen, the limited existence of treatment options and poor prognosis in this patient population, a decision was made to treat patients at a higher frequency of imetelstat administration for at least the first 12 cycles. There is a potential that neutropenia could be aggravated by the increased frequency of imetelstat. Therefore, the prophylactic use of antibiotics and antifungals has been recommended for use in patients according to local standards, especially when they are on the 1200 mg dosing. This prophylactic use of antimicrobials may also prevent infections as a reason for disease progression.

A risk benefit assessment will be performed after enrolling some patients as described in section 4.2.

Additional note:

The ongoing COVID-19 pandemic may affect the conduct and continuity of this clinical trial and may require implementation of temporary or alternative safety-related procedures or mechanisms. A designated guideline describing this mechanism will be provided to the participating sites and is part of the site training procedures.

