9.1.3 Serious adverse events (SAEs)

A serious adverse event (SAE) is classified as any untoward medical occurrence that at any dose (including overdose) meets the following seriousness criteria:

- Results in death
- Is life-threatening
- Requires inpatient hospitalization or prolongation of existing hospitalization*
- Results in persistent or significant disability or incapacity
- Is a congenital anomaly or birth defect

Important medical events that may not result in death, be life-threatening, or require hospitalization, or results in disability, may be considered serious based upon appropriate medical judgment, they may jeopardize the participant and may require medical or surgical intervention to prevent one of the outcomes listed in this definition. Medical and scientific judgment should be exercised every time in deciding whether such an AE should be considered serious.

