9.3.1 Events not to be treated as AEs

- Preplanned interventions or occurrence of endpoints specified in the study protocol are not considered AEs, if not defined otherwise (e.g. as a result of overdose)
- Medical or surgical procedures, e.g., surgery, endoscopy, tooth extraction, transfusion that are not associated with the indication under study. However, the event leading to the procedure is considered an AE. If this event is serious, the procedure must be described in the SAE narrative.
- Pre-existing disease or medical condition prior to the screening visit that does not worsen
- Situations in which an adverse event change did not occur. In addition, the following reasons for hospitalizations are not considered AEs, and therefore not SAEs:
 - Hospitalizations for cosmetic elective surgery, social and/or convenience reasons. Treatment, which were elective or pre-planned, treatments for a pre-existing condition that is unrelated to the indication under study and did not worsen.
 - Standard monitoring of a pre-existing disease or medical condition that did not worsen, e.g., hospitalization for coronary angiography in a subject with stable angina pectoris
 - Elective treatment of a pre-existing disease or medical condition that did not worsen, e.g., elective hip replacement for arthritis
 - Routine treatment or monitoring of the studied indication, not associated with any deterioration in condition
 - Admission to a hospital or other institution for general care, not associated with any deterioration in condition; or treatment on an emergency, outpatient basis for an event not fulfilling any of the definitions of serious and not resulting in hospital admission

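### One exemption in protocol section 9.2.2, read literally, removes new-onset hospital admissions from SAE reporting and contradicts sections 9.1.3 and 9.3.1

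*Protocol*

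**What the plan says.** Protocol 9.1.3 defines an SAE by a list of criteria, one of which is "Requires inpatient hospitalization or prolongation of existing hospitalization". Section 9.2.2 repeats that criterion ("requires inpatient hospitalization or prolongation of existing hospitalization") and then introduces a list of exceptions: "Hospitalization is a seriousness criterion. The following admission to hospitals should not be recorded and reported as an SAE". The list has four entries:

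- administrative admissions;
- admissions before consent;
- "Hospital admission not associated with a worsening of a preexisting condition";
- stays in which no AE occurred, such as planned care of the AML or MDS itself, with transfusions counted in.

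Section 9.3.1, on events not to be treated as AEs, covers similar ground in narrower terms. One of its exemptions is "Elective treatment of a pre-existing disease or medical condition that did not worsen, e.g., elective hip replacement for arthritis". Section 9.3.2 adds a separate exemption for events caused solely by progression of the underlying disease.

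Section 9.3 makes the investigator responsible for judging seriousness and points to section 9.1.2 for the criteria. Section 9.1.2 defines treatment-emergent AEs; the SAE criteria are in 9.1.3.

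**The concern.** The third entry lacks the words that would limit it. It does not say that the admission must be for a pre-existing condition, or that it must be elective or planned. An admission for something that began on study is, by definition, not a worsening of something already present, so it falls inside the exemption.

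The rule is applied at the site, before the sponsor sees the event. An event that the site does not class as serious triggers no 24-hour report under section 9.4. It cannot be assessed as a SUSAR, because section 9.1.5 requires seriousness. It also does not appear in the SAP's SAE listing.

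New acute events matter in this trial. Section 1.3.1 explains that dosing frequency was raised, accepts that neutropenia could become worse, and says of the experience so far: "The most frequently recorded AEs were under the following Medical Dictionary for Regulatory Activities (MedDRA) system organ classes: infections and infestations". Section 4.2 provides for no independent data monitoring committee, and the lead investigators carry out the risk/benefit assessment themselves.

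**Working it through.** No arithmetic applies. The check is to run typical admissions through each rule as written.

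| Admission during treatment | 9.1.3 and the criterion in 9.2.2 | Third entry of the 9.2.2 list, literal | 9.3.1 |
|---|---|---|---|
| New pneumonia, serious only because the patient is admitted | SAE | Exempt | Not exempt |
| Elective admission for an unchanged pre-existing condition | Not an untoward event | Exempt | Exempt |
| Admission because a pre-existing condition has worsened | SAE | Not exempt | Not exempt |

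The rules agree in the second and third rows and conflict in the first. Read literally, the entry keeps worsened old conditions reportable and exempts new events. Section 9.1.1 treats conditions that began after consent and conditions that worsened after consent alike, as AEs. The entry in 9.2.2 keeps only the second half of that pair.

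Next, does any other text settle the conflict?

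- The fourth entry of the list (admissions with no AE) hints at a narrower intent, but it is a separate exemption and does not limit the third.
- Section 9.3.2 exempts only events due solely to disease progression. It neither covers a new pneumonia of other cause nor restores it to reporting.
- The pointer in 9.3, which might have given the SAE definition priority, leads to 9.1.2, the TEAE definition.

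Last, what follows if a site applies the entry literally to the first row?

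- **Could be lost:** the 24-hour report (protocol 9.4), the SUSAR assessment (9.1.5, 9.5), and the entry in listing 16.7.2 (SAP 8.5.1).
- **Kept:** the AE record (protocol 9.3) and its CTCAE grade (9.2.1), AE listing 16.7.1 and, if treatment-emergent, the table of TEAEs by toxicity (SAP 8.5.1). If the event is related and grade 3 or higher, it also stays in the time-to-first-event analysis (SAP 7.7.13 and 8.5.2). None of these needs the SAE flag. AE details are also among the data that the section 4.2 review may use.

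**The case against.** The strongest reply is that nobody would read the entry this way. Taken literally, it would make the administrative and no-AE entries beside it largely redundant and would nearly cancel the criterion that introduces the list. Section 9.3.1 shows the evident intent, and section 9.4 requires every SAE to be reported within 24 hours. SAEs were in fact recorded: section 1.3.1 counts 30. This is a fair account of intent, and it makes widespread misreading unlikely. It does not remove the conflict, because no visible text limits the entry.

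Some material is also out of sight. The hospitalization item in 9.1.3 carries an asterisk whose note is not in the available text, and the Safety Management Plan holds further reporting detail. Either might clarify the point.

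A reader might infer three stronger claims, none of which the documents support:

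- **Every new-onset admission is exempt.** An event that is also life-threatening, fatal or medically important meets another criterion, and nothing says that the entry overrides those. Febrile neutropenia is a weak example. Entry requires at least one cytopenia, and in a patient already neutropenic the event may count as a worsening.
- **These events would be missing from the section 4.2 review.** They would lose SAE status but remain in the AE data.
- **A share of the 30 SAEs shows the size of the loss.** Those events were reported. The documents do not say how many were serious through hospitalization alone or how many were new. The statement about infections describes AEs, not those SAEs.

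**Conclusion.** The entry is wrong as worded and should be fixed. It conflicts with 9.1.3, with the criterion in its own section, and with the narrower wording of 9.3.1. The conflict concerns new events that are serious only through hospitalization. What is at risk for these is prompt SAE reporting, SUSAR assessment and the SAE listing; their record as graded AEs is not at risk.

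The size cannot be estimated from the documents, and nothing shows that any admission went unreported. The conclusion rests on the literal wording and on the absence of limiting text in the protocol and SAP as available. The primary endpoint and the efficacy analyses are unaffected.

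**What to change.** 1. Reword the third entry in 9.2.2 to: *Hospital admission for a pre-existing condition that has not worsened*. State the reference point for pre-existing and use the same one throughout. At present 9.1.1 counts from informed consent, while 9.3.1 counts from the screening visit.
2. In section 9.3, change the cross-reference for the seriousness criteria from 9.1.2 to 9.1.3.
3. Have monitors confirm, within the AE/SAE checks and source data verification already planned in section 11.4, that no admission was left unreported because of the present wording.

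The cost is two short text changes in the next protocol version or a clarification letter, plus one item on the monitoring checklist and any late SAE reports that it turns up. No endpoint, sample size, treatment rule or planned analysis changes.

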9.2.3 Relationship to IMP

All AEs and SAEs must have their relationship to IMP assessed by the investigator who examines and evaluates the study participant based on temporal relationship and clinical judgment. The degree of certainty about causality will be graded using the categories below:

Related – There is clear evidence to suggest a causal relationship, and other possible contributing factors can be ruled out. The clinical event, including an abnormal laboratory test result, occurs in a plausible time relationship to IMP administration and cannot be explained by concurrent disease or other drugs or chemicals. The response to withdrawal of the IMP (dechallenge) should be clinically plausible. The event must be pharmacologically or phenomenologically definitive, with use of a satisfactory rechallenge procedure, if necessary.

Probable Related – There is evidence to suggest a causal relationship, and the influence of other factors is unlikely. The clinical event, including an abnormal laboratory test result, occurs within a reasonable time after administration of the IMP, is unlikely to be attributed to concurrent disease or other drugs or chemicals, and follows a clinically reasonable response on withdrawal (dechallenge). Rechallenge information is not required to fulfill this definition.

Possible Related – There is some evidence to suggest a causal relationship (e.g., the event occurred within a reasonable time after administration of the IMP). However, other factors may have contributed to the event (e.g., the study participant's clinical condition, other concomitant events). Although an AE may rate only as "possibly related" soon after discovery, it can be flagged as requiring more information and later be upgraded to "probably related" or "definitely related", as appropriate.

Unlikely to be related – A clinical event, including an abnormal laboratory test result, whose temporal relationship to IMP administration makes a causal relationship improbable (e.g., the event did not occur within a reasonable time after administration of the IMP) and in which other drugs or chemicals or underlying disease provides plausible explanations (e.g., the participant's clinical condition, other concomitant treatments).

Not Related – The AE is completely independent of IMP administration, and/ or evidence exists that the event is related to another etiology. There must be an alternative, definitive etiology documented by the investigator.

9.2.4 Expectedness of IMP

The sponsor will be responsible for determining whether an SAE is expected or unexpected. An SAE will be considered unexpected if the nature, severity, or frequency of the event is not consistent with the risk information (most current version of IB) previously described for the

IMP.

9.3 Documentation and reporting of AE/SAE

All subjects will be monitored for AEs during the study by the study personnel. Assessments may include monitoring of any or all of the following parameters: the subject's clinical symptoms, laboratory, pathological, radiological or surgical findings, physical examination findings, or findings from other tests and/or procedures.

The investigator must assess all abnormal laboratory results for their clinical significance. If any abnormal laboratory result is considered clinically significant, the investigator must provide details about the action taken with respect to the test drug and about the event's outcome. All laboratory values have to be signed by the investigator.

For adverse events reporting the medical diagnosis must be reported. In case the diagnosis is not available, individual symptoms can be reported to fulfill reporting timelines. If a diagnosis becomes available at a later stage, it must be added to the reported event. In cases of surgical or diagnostic procedures, the condition/illness leading to such a procedure is considered as the AE rather than the procedure itself. In case of a fatality, the cause of death is considered as the AE, and the death is considered as its outcome. The Investigator shall make every effort to obtain a copy of the autopsy report and or death certificate and transmit this, after anonymization, to the sponsor.

Any medical condition that is present at the time that the participant is screened will be considered as baseline and not reported as an AE. However, if the study participant's condition deteriorates at any time during the study, it will be recorded as an AE.

All AEs (for example observed AEs, AEs mentioned upon open questioning by a member of the investigator's team or spontaneously reported AEs by the subject) will be recorded by the Investigator from the time the subject signs informed consent until 28 (\pm 5) days after the EOT visit (i.e. TEAEs) as well as those SAEs made known to the Investigator at any time thereafter that are suspected of being related to IMP (i.e. SADRs).

If the AE onset is prior to the first dose of IMP and the event does not increase in severity after initiation of IMP, the AE is then considered to be a pre-treatment AE and will not be reported in the TEAE incidence tables.

If the onset is prior to the first dose of IMP and the severity increases thereafter, the event is documented as a TEAE.

If the onset is after the first dose of IMP, the event is documented as a TEAE. This rule is consistent with the treatment-emergent signs and symptoms convention for counting AEs.

An exception will be if a patient experiences an SAE after signing informed consent but prior to receiving a study drug. In this case, the event will NOT be collected unless the investigator feels the event may have been caused by a protocol-required procedure.

The sponsor ensures that all persons involved in the treatment of study subjects are adequately informed about the responsibilities and actions required when AEs occur. Study subjects will be asked at each visit whether they have experienced AEs or SAEs. AEs will be documented in the study subject's medical records and in the (e)CRF.

The investigator is responsible for evaluating all AEs to determine whether seriousness criteria as defined in section 9.1.2 are met. AEs observed, mentioned upon open questioning by a

member of the investigator's team or spontaneously reported by the subject will be documented. In case of ongoing AEs after the last follow-up visit – especially when related to treatment with the IMP – the respective AE will be followed until resolution, if possible.

Important follow-up information should also be reported to the Sponsor when available. If relevant information is missing at the time of the initial SAE report, the reporter should provide it in follow-up SAE report(s). A follow-up report should contain new, updated or corrected information. The follow-up report should describe whether the event has resolved or continues, if and how it was treated including documentation of all supportive actions taken.

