5.1.5 Posttreatment follow-up (FU) period

All AEs will be recorded by the investigator from the time the subject signed the ICF until ■■■■■■■■ days after the last dose of IMP. Additionally, all serious AEs (SAEs) made known to the investigator at any time thereafter and are suspected of being related to imetelstat will also be documented. Therefore, at ■■■■■■■■ days the first FU visit will take place. For the second FU visit (=EOS) please refer to VII Schedule of assessments and procedures (part 3).

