9.1 Definitions of adverse events and adverse drug reactions

9.1.1 Adverse events (AE)

An adverse event (AE) is any untoward medical occurrence (i.e., any unfavorable and unintended sign [including abnormal laboratory findings], symptom or disease) in a patient or clinical investigation subject after providing written informed consent for participation in the study. Therefore, an AE may or may not be temporally or causally associated with the use of a medicinal (investigational) product.

A surgical procedure that was planned prior to the start of the study by any physician treating the subject should not be recorded as AE.

In the following differentiation between medical history and AEs, the term “condition” may include abnormal e.g., physical examination findings, symptoms, diseases, or laboratory or ECG test results.

- Conditions that started before signing of informed consent and for which no symptoms or treatment are present at the time of signing of informed consent are recorded as medical history.
- Conditions that started before signing of informed consent and for which symptoms or treatment are present after signing of informed consent, at unchanged intensity, are recorded as medical history.
- Conditions that started or worsened after signing of informed consent will be documented as adverse events.
- The term “disease progression” should be avoided when recording AEs. It is preferred that the diagnosis/signs/symptoms are used as the reported terms. Disease progression can be captured by the investigator as the alternative causality for the event.
- Instead of the term “infusion related reaction”, the signs and symptoms of the reaction should be captured to be able to characterize the event.

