9.2 Classification of AEs

9.2.1 Severity

The Common Terminology Criteria for Adverse Events (CTCAE) is used by default as severity grading scale AEs in cancer therapy, clinical trials, and other oncology settings. A grading (severity) scale is provided for each AE term. All appropriate treatment areas have access to a copy of the CTCAE current Version 5.0 in the investigator site file or as an electronic document provided by the sponsor (see Appendix VI, section 16.6). All serious adverse clinical experiences, whether observed by the investigator or reported by the patient, must be recorded, with details about the duration and intensity of each episode, the action taken with respect to the IMP, and the patient's outcome in a separate SAE-document. The investigator must evaluate each adverse event for its seriousness and for its relationship to the IMP.

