9.4 Investigator reporting responsibilities

The investigator must keep copies of all AE information, including correspondence with the sponsor and the EC/IRB, on file. The investigator will be responsible for notifying regulatory bodies and ECs/CECs/IRBs as locally required.

The Investigator is obligated to report any SAE/pregnancy to the Sponsor within **24 hours** of becoming aware of the event to ensure the safety of all participants in the study and to meet regulatory reporting requirements. Although all information required for completion of an SAE report form may not be available within the specified time period, an initial report should be submitted with the available information. Any new information obtained about the serious adverse event must be added to the existing eCRF form.

The investigators report all occurring events electronically by completing the designated page in the eCRF system. A backup paper report form is provided to all sites as well. In case the eCRF cannot be accessed for any reasons, the SAE should be reported by completing and signing the paper backup form. The signed form will then be sent to:

Address: [REDACTED]
[REDACTED]
[REDACTED]
Phone: [REDACTED]
Fax: [REDACTED]
Email: [REDACTED]

Information on the form must be transferred to the eCRF by the site when it is accessible again. Each SAE and pregnancy must be followed up until resolution or stabilization by submission of updated reports (FU-report) to the designated recipient.

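### Protocol 9.3 drops serious events between consent and first dose while keeping non-serious ones, which conflicts with five other provisions and can leave the TEAE rule without a pre-dose onset and grade

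*Protocol*

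**What the plan says.** The general rule in Protocol 9.3 is that adverse events "will be recorded by the Investigator from the time the subject signs informed consent until 28" (± 5) days after the EOT visit. Later in the same section comes a carve-out: "An exception will be if a patient experiences an SAE after signing informed consent but prior to receiving a study drug". Its effect is then stated: "In this case, the event will NOT be collected unless the investigator feels the event may have been caused by a protocol-required procedure". It applies to serious events only.

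Other provisions have no such carve-out and do not refer to it:

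- Protocol 5.1.5, repeated in SAP 2.1.5: "All AEs will be recorded by the investigator from the time the subject signed the ICF until" a set number of days after the last dose.
- Protocol 9.1.1: "Conditions that started or worsened after signing of informed consent will be documented as adverse events". Medical history is reserved there for conditions that began before consent.
- Protocol 9.2.1: "All serious adverse clinical experiences, whether observed by the investigator or reported by the patient, must be recorded".
- Protocol 9.4: "The Investigator is obligated to report any SAE/pregnancy to the Sponsor within" 24 hours.

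For analysis, Protocol 9.3 treats an event as pre-treatment, and keeps it out of the TEAE incidence tables, on this condition: "If the AE onset is prior to the first dose of IMP and the event does not increase in severity after initiation of IMP". An event with onset after the first dose is a TEAE, and so is one with earlier onset that becomes more severe. SAP 7.7.12 likewise depends on whether the event was already present and whether it worsened. Toxicity is measured by TEAEs (SAP 6.2.2), and only TEAEs are counted (Protocol 10.9.3).

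**The concern.** Within one screening window the plan keeps the non-serious events and discards the serious ones, with no stated reason. That creates two problems.

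The first is operational. A site with a patient admitted during screening is told by 9.3 not to collect the event and by 9.4 to report it within 24 hours. Sites may resolve this differently, so the completeness of pre-dose safety data could vary between them.

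The second is analytical. Treatment-emergent status is a comparison with the pre-dose state. In a single-arm trial without concurrent controls, that state is the only within-patient background against which later events can be read. If a serious pre-dose event is missing from the AE data, an event that was already there may look new. It could then enter the TEAE tables. It could also enter the time to first related TEAE of grade 3 or higher (SAP 7.7.13) if its grade is 3 or more and it is judged related. SAP 7.7.12 adds that a missing causality assessment is classed as related.

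**Working it through.** There is no figure in the plan to reproduce, so the check sets the rules side by side and follows cases through them.

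**Step 1. What each provision requires for a serious event after consent, before first dose, with no suspected link to a study procedure**

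| Provision | Requirement |
|---|---|
| Protocol 9.3, general rule | Record (all AEs from consent) |
| Protocol 9.3, exception | Do not collect |
| Protocol 5.1.5 and SAP 2.1.5 | Record (all AEs from ICF signature) |
| Protocol 9.1.1 | Document as an AE |
| Protocol 9.2.1 | Record (all serious experiences) |
| Protocol 9.4 | Report to the sponsor within 24 hours |

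One provision says no. The others say yes and do not mention the exception.

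**Step 2. Length of the window.** Screening procedures take place within 35 days before treatment starts (Protocol 5.1.1), so the exception can apply for up to 35 days per patient.

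**Step 3. Follow each type of event to the TEAE tables, assuming the site obeys the exception**

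- *Non-serious, starts in screening, unchanged after dosing.* Recorded with pre-dose onset and grade, and kept out of the TEAE tables.
- *Serious, study procedure suspected.* Collected and handled in the same way.
- *Serious, no procedure suspected, resolved before dosing.* No TEAE arises. The loss is confined to the record of serious events.
- *Serious, no procedure suspected, patient never dosed.* Outside the Safety Evaluation Set, so no TEAE can arise.
- *Serious, no procedure suspected, worsens after dosing.* A TEAE whether or not the earlier phase was collected.
- *Serious, no procedure suspected, continues unchanged after dosing.* No AE entry exists from before the first dose. If the site later enters the event with its true onset, 9.3 classes it as pre-treatment. If it is entered with an onset after the first dose, nothing in the AE data contradicts that, and it becomes a TEAE.

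Only the last case, in its second branch, misclassifies an event. It arises because the rule needs an onset and a severity that the exception tells the site not to collect.

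**Step 4. Could another form supply them?** Protocol 8.2.1.2 asks for current medical conditions at screening, and 9.3 treats a condition present when the patient is screened as baseline. Either may catch a condition already present at the screening visit. An event that begins later in the window is not clearly covered, because 9.1.1 sends post-consent onsets to the AE record. SAP 7.5.1 describes CTCAE grading for adverse events and mentions no grade for medical history.

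**The case against.** The strongest reply is that the exception is deliberate and labelled. It follows directly on the general rule, and a specific exception normally qualifies a general statement. It keeps the pre-dose serious events that study participation could have caused, and the rest precede any imetelstat exposure. This explains what 9.3 intends. It does not reconcile 9.3 with 9.2.1 and 9.4, which are separate duties stated without reference to it, and it does not supply the onset and grade that the TEAE rule uses.

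Several further points stand and limit the consequence. Exclusion criteria 6, 8, 9 and 11 (recent major surgery, significant cardiac disease, uncontrolled infection requiring IV antibiotics, life-threatening illness) will remove some of these patients before dosing. Where an event leads to screening failure, Protocol 6.6 requires the reason for not qualifying in the eCRF. The Safety Management Plan, to which 9.3.2 refers, is not available here and may define how the exception works in practice.

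A reader might infer that the most severe pre-treatment conditions go unrecorded. The documents do not support that. Seriousness is not CTCAE grade, so a non-serious grade 3 event before dosing is still collected. Source records exist, and conditions present at screening may have a baseline entry. What may be missing is an AE/SAE entry for some serious events.

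A reader might also infer that the later course of these events will be reported as imetelstat toxicity. That requires an event that persists unchanged and is entered with an onset after the first dose. For the grade 3 endpoint it also requires a related or missing causality judgement.

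**Conclusion.** The conflict is established from the text: Protocol 9.3 excludes serious pre-dose events that Protocol 5.1.5, 9.1.1, 9.2.1 and 9.4 and SAP 2.1.5 require to be recorded or reported. The effect on TEAE classification is a possibility, confined mainly to serious events that persist unchanged past the first dose. It rests on the assumption that sites follow the exception and that no other entry carries the true onset and grade.

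The number of patients affected cannot be estimated. It is tempting to multiply an assumed monthly rate of serious events by the length of screening and the number treated. The documents give no such rate, and the planned number of subjects is redacted. The product would also include patients who become ineligible, events that resolve before dosing, and procedure-related events that are still collected. The response endpoint is not affected. The point concerns the safety record, and the passages should be reconciled.

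**What to change.** Remove the exception in Protocol 9.3 as a rule about collection. Record every serious event from consent in the eCRF with onset date and CTCAE grade, and flag it as pre-treatment. Then apply the rule 9.3 already contains, under which such events stay out of the TEAE tables unless they worsen after the first dose.

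If the sponsor wants to limit paperwork for events before exposure, keep the exception only for expedited reporting on the SAE form. Section 9.3.2 already takes that approach for certain other events.

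Align Protocol 5.1.5, 9.1.1, 9.2.1, 9.3 and 9.4 and SAP 2.1.5 so that they state one rule, and check the Safety Management Plan against it.

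The cost is an amendment to wording and a few extra eCRF entries. No planned analysis changes.
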